**Duration of Study:**

The study will include 3 periods: screening period (up to 7 days), treatment period (up to 14 days), and a follow-up visit (approximately on Day 28 ( $\pm 3$  days) or 14 ( $\pm 3$ ) days after the last dose for those who are discharged from the hospital before Day 14).

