### **7.2.1. Follow-up for Patients Who Discontinued from Treatment/Study**

If the patients are discharged from the hospital before Day 14, it is preferred that the follow-up visit is in person to obtain safety laboratory tests and blood samples for biomarker analysis as well as clinical outcome data. However, infection control or other restrictions may limit the ability of the patients to return to the clinic. In this case, the follow-up visit may be conducted by phone and only safety data will be obtained.

Patients who complete the 14-day treatment should be instructed to have the scheduled follow-up visit on Day 28. If a patient determines he/she no longer wishes to participate in follow-up visit, all the procedures associated with Day 28/Early Discontinuation/End of Study (EOS) visit should be completed at the time of discontinuation.

In both cases, follow-up for AEs should occur as per the discretion of the investigator. It is vital to obtain follow-up data on any patient withdrawn because of an AE or SAE. In every case, efforts must be made to undertake protocol-specified safety follow-up procedures.

Refer to the schedule of assessments (SoA) for data to be collected at the time of study discontinuation, follow-up, and for any further evaluations that need to be completed.

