#### **9.9. Follow-up Visit on Day 28/End of Study (EOS)**

- Vital signs
- 12-lead ECG
- Routine clinical laboratory tests including [REDACTED] one at local laboratory
- Coagulopathy and cardiac function panels done at local laboratory
- Urinalysis
- Oxygen use and saturation (pulse oximetry)
- WHO ordinal scale
- AE/SAE assessment and concomitant medications/current procedures

If the patients are discharged from the hospital before Day 14, all the assessments planned for Day 14 should be carried out before discharge. If a patient is still hospitalized after Day 14, no study drug will be administered after the last dose on Day 14.

It is preferred that the follow-up visit is in person to obtain safety laboratory tests. However, infection control or other restrictions may limit the ability of the patients to return to the clinic. In this case, the follow-up visit may be conducted by phone and only safety data will be obtained. Study drugs will not be administered for early discharged patients.

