Informed consent	X									
Medical history	X									
Demographics	X									
Physical examinations	X ⁴								X	
Vital signs ⁵	X	X	X	X	X	X	X	X		X

12-lead ECG	X	X ⁶		X		X		X	X
Blood samples for routine lab tests including CRP and ferritin ⁷	X	X	X	X	X	X	X	X	X
Blood samples for coagulopathy and cardiac panels ⁸		X	X	X		X		X	X
Urine sample for urinalysis	X	X	X	X		X		X	X
Serum serology and pregnancy tests for screening	X								
Inclusion and exclusion	X								
Randomization		X							
Treatment		X	X	X	X	X	X	X	
Oxygen use and saturation (pulse oximetry)	X	X	X	X	X	X	X	X	X
PaO ₂ /FiO ₂ ratio	X	X		X				X	
WHO ordinal scale		X		X				X ¹³	X
Blood sample for cytokine/chemokine panels and CV biomarkers ⁹		X		X				X	
Blood sample for PK analysis and pRIP1/pMLKL assay ¹⁰		X		X				X	
Urine sample for NGAL and KM-1 assay ¹¹		X		X				X	
AE and ConMed	X	X	X	X	X	X	X	X	X

1. Enrollment and Baseline. Screening and Baseline visits can be combined. ECG, laboratory test and other test results taken within 24 hours prior to consent will be used as Baselines.
2. End of Treatment (EOT) or early discharge.
3. End of the study (EOS) or early discontinuation.
4. For enrolled patients, physical examination obtained at screening will be the Baseline. Weight and height will be measured at screening.
5. Vital signs will be taken before the 1st dose on Day 1 as Baseline, and within 3 hours before the 2nd dose on other days.
6. Three ECGs with 1-3 min interval before the 1st dose on Day 1 only, and the means of the 3 ECGs will be used as Baselines. ECGs will be done within 3 hours before the 2nd dose on other days. Local ECG machine will be used in this study.
7. Routine laboratory tests before the 2nd dose will be done daily at local labs. CRP and ferritin tests will be done on Days 1, 3, 7, 10 and 14.
8. Coagulopathy panel including D-dimer, fibrinogen, PT, PTT and INR, and cardiac function panel including NT-proBNP (or BNP) and high-sensitivity cardiac troponin will be done on Days 1, 3, 7, 10 and 14 at local labs with samples collected before the 2nd dose.
9. One blood sample collected before the 1st dose on Day 1 and before the 2nd dose on Days 7 and 14 for cytokine/chemokine panels and CV biomarker assays to be conducted at a central lab

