4 STUDY DESIGN AND PLAN

This is a multicenter, randomized, double-blinded, placebo-controlled study to evaluate safety and efficacy of SIR1-365 in hospitalized patients with severe COVID-19. The primary objective is to assess the overall safety and tolerability of SIR1-365 administered orally at 100 mg, 3 times per day (TID) for up to 14 days relative to the placebo group. The secondary objectives are to assess the effects of SIR1-365 on clinical efficacy endpoints and the biomarkers indicative of inflammation, target engagement, and kidney injury as well as SIR1-365 PK.

Approximately 60 eligible patients will be randomly assigned at a 1:1 ratio to receive either SIR1-365 at 100 mg TID or matching placebo for up to 14 consecutive days. For ethical and medical reasons, standard-of-care treatments for COVID-19 will be provided to all patients. Thus, the study drugs (either SIR1-365 or matching placebo) will be given as add-on therapy.

Patients could be hospitalized for up to 14 days. Patients will be assessed daily while hospitalized. If the patients are discharged from the hospital before Day 14, no study drugs will be administered. A follow-up visit in person will be performed to obtain safety laboratory tests and blood samples for biomarker analysis as well as clinical outcome data. However, infection control or other restrictions may limit the ability of the patients to return to the clinic. In this case, the follow-up visit may be conducted by phone and only safety data will be obtained. Follow-up visit will be scheduled approximately on Day 28 (± 3) or 14 days after discharge/end of treatment.

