6.2. Analysis Set

All patients who receive study drug without major protocol deviation related to PK/PD analysis and have sufficient PK/PD data to obtain reliable estimates of the key PK/PD variables. Treatment assignment will be based on the treatment actually received.

If a sample yields invalid assay results for all the biomarkers, the data will not be imputed. If a sample has both valid and invalid assay results, the biomarkers with failed assay will be imputed by the overall mean of the same biomarker measured at the same time point within the same treatment group. If the assay passed QC but the result is BLQ, it will be imputed as 0. This process is shown by the flow chart below.

All plasma drug levels below the limit of quantitation (BLQ) values will be imputed as zero (0). If a sample yields invalid assay result, the data will not be imputed. The process is shown by the flow chart below.

For the analysis of both PK and PD biomarker data, if the sample was collected before or on Day 7, the time is labelled as Day 7; if the sample was collected after Day 7, the time is labelled as Day 14.

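### The PK/PD plan labels samples Day 7 or Day 14 by calendar day alone, so any late or follow-up marker sample would be counted as Day 14

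*SAP*

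**What the plan says.** **The label rule.** PK/PD plan 6.2 covers drug levels and markers alike. A sample up to and including Day 7 is Day 7; for later ones, "if the sample was collected after Day 7, the time is labelled as Day 14". Neither 6.2 nor 6.4 says which value to use when two samples share a label.

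**Where the label is used.** Section 6.4 applies one-sample and two-sample t-tests to the change from baseline at Day 7 and Day 14. In 6.2, a marker whose assay failed in an otherwise valid sample is "imputed by the overall mean of the same biomarker measured at the same time point within the same treatment group".

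**Follow-up blood.** Section 4 of the same plan, after describing early discharge, says: "A follow-up visit in person will be performed to obtain safety laboratory tests and blood samples for biomarker analysis". It times the visit at about Day 28 (±3) or "14 days after discharge/end of treatment". Protocol 7.2.1 states a preference for patients discharged before Day 14: "it is preferred that the follow-up visit is in person to obtain safety laboratory tests and blood samples for biomarker analysis". The Protocol Synopsis puts that visit 14 (±3) "days after the last dose for those who are discharged from the hospital before Day 14".

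**The schedule.** In SAP Table 5.2 the row "Blood sample for cytokine/chemokine panels and CV biomarkers" is marked on Days 1, 7 and 14 only. The Day 14/EOT column has a ±2-day window; the Day 7 column has none. Protocol 9.9 says of the last visit "It is preferred that the follow-up visit is in person to obtain safety laboratory tests", and its list contains no central-laboratory marker draw.

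**The concern.** The rule looks built to place end-of-treatment sets, which can fall on either side of Day 7 when a patient goes home early. For that purpose it works. Its reach is wider than its purpose, because everything after Day 7 is Day 14, however late and whatever the visit.

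If a site draws the plan's own markers at follow-up, an off-drug, post-discharge value is counted as Day 14. That would dilute any drug effect and add recovery after discharge to the within-arm change. If the arms are discharged at different rates, it would also bias the between-arm comparison. The same label sets the mean used for imputation. The plan describes its analyses as fixed before unblinding, so leaving such a sample out later would be an unplanned choice. Effects on inflammatory and cardiovascular markers are secondary objectives.

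**Working it through.** The plan gives no figure on this point, so there is none to reproduce. The check applies the rule to the sampling the documents describe.

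**1. Labels.** Take the last dose as falling on the discharge day *d*. Follow-up then runs from *d* + 11 to *d* + 17.

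| Last dose | End-of-treatment set labelled | Follow-up window | Follow-up labelled | Values labelled Day 14 |
|---|---|---|---|---|
| Days 1–7 | Day 7 | Days 12–24 | Day 14 | follow-up only |
| Days 8–13 | Day 14 | Days 19–30 | Day 14 | two, no rule to choose |
| Day 14 | Day 14 | Days 25–31 | Day 14 | two, if drawn |

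The last row is the least likely, since both texts that mention follow-up biomarker blood do so in the setting of early discharge.

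**2. Off drug.** The Protocol gives a half-life of about 6–7 hours and no dosing after discharge. Eleven days at 7 h is 11 × 24 / 7 = 37.7 half-lives; 17 days at 6 h is 17 × 24 / 6 = 68.

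**3. Slipped Day 7 draw.** Taken on Day 8, it is labelled Day 14. The patient then has no Day 7 value and, if sampled again at end of treatment, two Day 14 values. This needs no follow-up sample.

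**4. Would follow-up samples exist?** Section 4 and Protocol 7.2.1 say or prefer yes. The schedule and Protocol 9.9 list none, and 7.2.1 itself refers the reader to the schedule for what to collect. Follow-up biomarker blood could also mean CRP and ferritin, which the schedule does mark at follow-up and the main SAP analyses. On the other hand, section 3 of the PK/PD plan lists its biomarker measures without those two. The count is therefore unknown and may be zero.

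**5. Which series.** The t-test table has 30: 11 cytokines + 6 chemokines + 3 cardiovascular markers = 20 serum series, 2 urine markers, and 8 pRIP1/pMLKL series. Only the serum rows have no dose anchor and could take a follow-up blood sample as they stand.

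**6. Illustrations under assumed shares.** These are not estimates.

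*Dilution.* Assume 30 per arm, a true effect of 0.7233 SD (chosen to give 80% power), no effect left at follow-up, and a share *f* of Day 14 values that are follow-up values. The noncentrality is 0.7233(1 − *f*)√(30/2).

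| *f* | Noncentrality | Power, values kept | Power, values excluded (n = 30(1 − *f*)) |
|---|---|---|---|
| 0% | 2.80 | 80% | 80% |
| 10% | 2.52 | 71% | 76% |
| 20% | 2.24 | 61% | 71% |
| 40% | 1.68 | 39% | 58% |

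*Double counting.* Suppose a share *g* of patients contribute two values with correlation ρ, and both are entered as independent. The true variance of an arm mean is then 1 + 2*g*ρ/(1 + *g*) times the assumed one. For *g* = 0.2 and ρ = 0.5 this is 1 + 0.2/1.2 = 1.167, so the type I error is about 2Φ(−1.96/√1.167) = 7%. For *g* = 0.5 it is 1.333, giving 9%. Over ρ = 0.3 to 0.7 the ranges are 6–8% and 7–11%; simulation gave the same.

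**The case against.** The best defence is that sites following the protocol produce nothing for 6.2 to mislabel. Protocol 7.2.1 defers to the schedule, Protocol section 8 calls adherence to it essential, and the schedule has no central-laboratory marker draw at follow-up. Section 4 of the PK/PD plan is design background; its objectives, sampling section and table shells know only baseline, Day 7 and Day 14. A follow-up visit by phone yields safety data only. A patient sampled on schedule after Day 7 has one Day 14 set, so no tie-break is needed.

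Most of this stands, and it limits the size of the point. It does not remove it. The rule is stated, not merely incomplete, and it gives a wrong label whenever a follow-up sample, an extra sample or a Day 8 draw exists. Section 5.1 allows additional PK time points, and the schedule's ±2 days around Day 14 is not carried into 6.2. The flow charts mentioned in 6.2 are not visible in the public text, but the text ties them to failed assays and values below quantitation, not to visit windows.

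A reader might infer more: that the 20 serum series are plainly contaminated, or that Day 14 power is really lost. The documents do not support that, because nothing shows that any such sample will be taken. Nor do they support extending the point to PK or target engagement. The PK rows are tied to a dose and pRIP1/pMLKL are split into predose and post-dose, so a sample with no dose fits neither. Finally, SAP section 6 names CRP when it speaks of estimates for later studies, and CRP lies outside this plan.

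**Conclusion.** The point holds as a minor defect of a stated rule. Section 6.2 sorts samples by calendar day only, without an upper bound, a visit key or a tie-break. If marker blood is drawn at follow-up, an off-drug value from 11 to 17 days after the last dose becomes a Day 14 value. It would be the only one for a patient discharged by Day 7, and a possible duplicate for one discharged on Days 8 to 13. A Day 7 draw taken on Day 8 is mislabelled too.

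The number of samples affected is unknown and may be zero. The power and type I figures rest entirely on an assumed share, an assumed effect and complete loss of effect at follow-up. The type I figures further assume that an analyst enters both values as independent, which the plan does not say. The study is not powered for these tests, and the primary adverse-event outcome is untouched.

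**What to change.** In PK/PD plan 6.2:

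- Label each sample by its scheduled visit. Define Day 14 as the Day 14/end-of-treatment/early-discharge set taken after Day 7 and no later than Day 16, the end of the schedule's window. A day limit alone is not enough: for a last dose on Days 1 to 5 the follow-up window opens on Days 12 to 16.
- If a patient has more than one sample under a label, use the scheduled-visit sample; for Day 14, that is the end-of-treatment one.
- Label follow-up and extra samples separately and keep them out of the Day 14 tests and imputation means.

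In PK/PD plan section 4 and Protocol 7.2.1, state whether follow-up blood includes the central-laboratory markers, and make both agree with the schedule.

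The cost is a few sentences. Because the PK and target-engagement rows are already tied to dosing, no extra table or sensitivity analysis is needed. The downside is possibly a few fewer values labelled Day 14, with none for patients discharged by Day 7.

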6.3. Statistical Analysis of PK Data

Summary statistics will be reported by treatment group for each sampling time point (D1 30 minutes predose, D1 2hr post dose, D7 30 mins predose, D7 2hr post dose, D14 30 mins predose, D14 2hr post dose). Summary statistics include N, mean, median, SD, Min, and max. The plasma drug concentration will be presented by line plots, which illustrate the mean +/- stderr for two groups.

6.4. Statistical Analysis of Biomarker Data

For each marker, raw signal value, change from baseline, and percentage change from baseline will be analyzed. Summary statistics (for raw signal measurements, change from baseline, and percentage change from baseline) will be reported for each marker at baseline, Day 7, and Day 14 by treatment group.

Line plots of change and percentage change from baseline will be presented for each marker. Each line illustrates the value of a PD marker (Y-axis) changes over time (X-axis) of a single subject. Each marker will be represented by one line plot, in which all the subjects are included, treatment groups will be labelled by different colors. In addition, mean +/- stderr line plots will be generated for the two treatment groups.

For pRIP1 and pMLKL, similar line plots will be presented for pre-dose and post-dose separately. Specifically, Day 1 pre-dose and Day 1 post-dose values will be used, respectively, as the baseline for the calculation of the change from baseline for pre-dose and post-dose plots.

One-sample t-test will be used to evaluate if the change from baseline (Day 7 and Day 14 respectively) is significant (i.e., if the change is different from zero). This will be performed for each treatment group separately. Two-sample t-test will be performed to evaluate if the change is different between the two treatment groups. Test will not be performed on percentage change.

Boxplots will be used to graphically represent the data in the 1-sample and 2-sample tests, the test p-value will be displayed in the boxplots.

Heatmap will be used to visualize the percent change of the all the markers (by marker types) for all the subjects.

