## 2.4. Summary of Clinical Data

The following studies have been completed in Australia:

- A randomized, double-blinded, placebo-controlled SAD study and MAD study were conducted in Australia to evaluate the safety, tolerability and PK of SIR1-365 in healthy adult volunteers. The results demonstrated that a single oral administration of SIR1-365 at 10, 30, 100, 300 and 600 mg and multiple doses at 50 mg TID, 100 mg TID, 200 mg TID were safe and well tolerated by the study subjects. The reported AEs were mild to moderate events with no need of intervention and resolved in a few days. No subject discontinued from the study. PK data showed a good dose proportionality of plasma SIR1-365 concentrations at the 5 single dose and 3 multiple dose cohorts in healthy volunteers. Peak plasma exposure was achieved around 1-2 hours after dose, and the half-life ( $T_{1/2}$ ) was around 6-7 hours depending on the doses.
- A randomized, open-label, single-dose, 2-way crossover study was conducted to assess the effect of food on bioavailability of SIR1-365 tablet after a single oral dose at 100 mg. The results of this study demonstrated that food does not significantly affect the bioavailability of SIR1-365 after oral administration. Thus, SIR1-365 oral tablets can be administered before or after meal.
- An open-label study was conducted to assess the PK profile of SIR1-365 given as an oral disintegrated suspension. The results of this study demonstrated that the plasma SIR1-365 concentrations-time curves and PK parameters were comparable when SIR1-365 was administered at a single oral dose of 100 mg either as a disintegrated suspension in the suspension PK study or as a solid tablet in the SAD study. Thus, SIR1-365 tablets can be administered as a disintegrated suspension via a gastric tube in those patients who cannot swallow the tablets.

- An open-label study was conducted to assess possible inhibitory effects of SIR1-365 on the activities of CYP450 isoforms 2C19 in healthy volunteers using sensitive index substrate omeprazole. The results of this study demonstrated that SIR1-365 can inhibit the activity of CYP450 isoform 2C19. Thus, medications that are mainly metabolized via CYP450 isoform 2C19 should be excluded in patient studies.

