## **8.4. PK Analysis**

Approximately 60 patients enrolled in the study will have peak and trough blood samples obtained within 30 min before and 2 hours ( $\pm 5$  min) after the 1st dose on Day 1, respectively. On Days 7 and 14, one blood sample will be collected within 30 min before and 2 hours ( $\pm 5$  min) after the 2nd dose, respectively.

Samples may be collected at additional time points during the study if warranted and agreed upon between the Investigator and the Sponsor. Instructions for the collection and handling of biological samples will be provided by the Sponsor. The actual date and time (24-hour clock time) of each sample will be recorded.

Plasma drug concentrations of SIR1-365 and metabolites will be summarized using descriptive statistics. Additional details for plasma concentration assessment will be included in a separate PK analysis plan. The PK analysis plan will supersede the protocol.

Drug concentration information that may unblind the study will not be reported to investigative sites or blinded personnel.

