## 10.3. Statistical Analyses

A detailed SAP will be developed and finalized before database lock.

A 2-sided alpha-level of 0.05 will be used for construction of confidence intervals. No adjustment for multiple endpoints will be employed. Although the study is not powered for hypothesis testing,

p-values will be generated to aid interpretation in addition to confidence intervals about the estimates.

The safety population will be the primary population for safety analysis. Analyses will be performed on observed data.

For clinical efficacy endpoints, the primary analysis will be in the ITT population. Rules for addressing missing data will be detailed in the statistical analysis plan. Sensitivity analyzes for the clinical efficacy endpoints may be performed in the mITT and/or PP populations.

The mITT population will be primary population for the biomarker analysis with exception of time to 50% reduction of CRP levels for which the ITT population will be primary. Sensitivity analyses incorporating imputation for missing biomarker values may be performed.

In general, baseline for each parameter is the last non-missing value collected prior to the first dose of study medication including pre-dose measurements made on the date of the first dose of study medication.

All data analyses will be conducted using SAS® (SAS Institute, Inc, Cary, North Carolina) software. In general, for descriptive summaries, continuous variables will be summarized using the mean, standard deviation, median, minimum value, and maximum value. Categorical variables will be summarized using frequency counts and percentages. All data will be presented in data listings.

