1 INTRODUCTION

This document outlines the statistical methods to be implemented during the analyses of data collected within the scope of SIR365-US-101 (A Multicenter, Randomized, Double-Blinded, Placebo-Controlled Study to Assess Safety and Efficacy of SIR1-365 in Patients with Severe COVID-19). This document excludes detail on the analysis of pharmacokinetic (PK)/pharmacodynamics (PD) endpoints, which will be detailed in a separate PK/PD analysis plan. The analyses excluded are the following:

- Serum Levels of Cytokines
- Serum Levels of Chemokines
- Biomarkers Indicative of Target Engagement
- Biomarkers Indicative of Kidney Injury
- Biomarkers Indicative of CV Endothelial Cell Damage
- Plasma Concentration of Study Drug

The purpose of this plan is to provide specific guidelines for the statistical analyses. Any deviations from this plan will be documented in the clinical study report (CSR).

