10. One blood sample will be collected from each patient within 30 min before and 2 hours (± 5 min) after the 1st dose on Day 1, respectively. On Days 7 and 14, one blood sample will be collected within 30 min before and 2 hours (± 5 min) after the 2nd dose, respectively. Each plasma sample will be divided into 4 parts, 2 for PK analysis and 2 for plasma pRIP1/pMLKL assay conducted at a central lab. PBMC preparation will be done at the sites with necessary equipment according to the laboratory manual for pRIP1/pMLKL assay.
11. About 10 mL of urine sample will be collected before dosing on Day 1, and in the morning on Days 7 and 14 for NGAL and KIM-1 assay to be conducted at a central lab
12. If the patients are discharged from the hospital before Day 14, all the assessments planned for Day 14 should be carried out before discharge. Study drugs will not be administered in early discharged patients. It is preferred that the follow-up visit is in person to obtain safety laboratory tests. However, infection control or other restrictions may limit the ability of the patients to return to the clinic. In this case, the follow-up visit may be conducted by phone and only safety data will be obtained. If a patient is still hospitalized after Day 14, no study drug will be administered after the last dose on Day 14.
13. When completing the WHO Ordinal Scale at Day 14/ EOT, if the subject has received physician orders to be discharged from the hospital, the score should be a 3 or less (*no longer hospitalized*).

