8.2 Standard Calculations

Variables requiring calculations will be derived using the following formulas:

- Baseline: A Baseline value, unless specified otherwise, is the last non-missing value recorded prior to the first dose of study drug.
- Study day: For a given date, study day will be calculated as the number of days from the day of first dosing of study drug, labeled day 1, therefore:

Study day = date of event/measurement - date of first dose of study drug + 1, for events/measurements on or after first dose

Study day = date of event/measurement - date of first dose of study drug, for events/measurements before first dose

- Durations (days): Durations, expressed in days, will be calculated as follows:

Duration in days = (Stop date/time of event – Start date/time of event)/(3660x24)

If the stop or start time is missing, only the date information will be used as follows:

Duration in days = Stop date of event – Start date of event + 1

- Height: Height entries made in inches are converted to centimeters using the following formula:

Height (cm) = Height (in) × 2.54

- Weight: Weight entries made in pounds are converted to kilograms using the following formula:

Weight (kg) = Weight (lb)/2.2046

- Body Mass Index (BMI): BMI is calculated using height and weight and is calculated using the following formula:

BMI (kg/m²) = Weight (kg) / [[Height (cm) / 100]²]

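### The post-dose pRIP1/pMLKL change plots take an on-treatment sample as baseline, and no baseline is named for the matching post-dose t-tests and summary tables

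*SAP*

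**What the plan says.** The PK/PD analysis plan is the second part of the SAP document, with its own section numbering. For the pRIP1 and pMLKL line plots, its section 6.4 states that "Day 1 pre-dose and Day 1 post-dose values will be used, respectively, as the baseline". The same sentence limits this rule to plots; it ends with the words "for the calculation of the change from baseline for pre-dose and post-dose plots". The next paragraph of 6.4 sets a one-sample t-test within each arm and a two-sample t-test between arms on change from baseline at Day 7 and Day 14. It does not say which Day 1 sample is the baseline.

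The schedule footnote in main SAP section 5 (Table 5.2, footnote 10) puts the Day 1 samples within 30 minutes before and 2 hours after the first dose. Each plasma sample is split into four parts, "2 for PK analysis and 2 for plasma pRIP1/pMLKL assay conducted at a central lab". On Protocol section 2.4, "Peak plasma exposure was achieved around 1-2 hours after dose".

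Two general baseline rules exist outside the PK/PD plan:

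- Protocol section 10.3: "In general, baseline for each parameter is the last non-missing value collected prior to the first dose of study medication".
- Main SAP section 8.2: "A Baseline value, unless specified otherwise, is the last non-missing value recorded prior to the first dose of study drug". Section 1 of that SAP, however, leaves "Biomarkers Indicative of Target Engagement" to the separate PK/PD plan.

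The PK/PD plan has no general baseline definition of its own. The outcome listed for both markers, in main SAP section 4 and PK/PD plan section 3, is change from Baseline to Day 7 and Day 14.

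**The concern.** A baseline is meant to be an untreated reference. In the active arm the 2-hour sample has already seen the drug at about its peak level, while in the placebo arm it has not. Subtracting it removes drug effect from one arm only. The post-dose plot then answers whether the post-dose level moves after the first dose. It does not answer whether the drug engages its target.

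If the t-tests follow the same rule, a null post-dose p-value could be read as no engagement when it means no further change since the first dose. If they follow the protocol's general rule instead, the plots and the tests differ while both are called change from baseline. Leaving this open also leaves a choice to be made after unblinding, which sits badly with the statement in section 6.1 of the PK/PD plan that its analyses are defined beforehand.

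**Working it through.** The documents give no effect size, SD or power for these markers, so there is no planned figure to reproduce.

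**1. What each baseline estimates.** Let E1 be the active-minus-placebo effect at 2 hours on Day 1, and E7 the same effect post-dose on Day 7. Randomisation makes the expected pre-dose difference zero.

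- Day 1 pre-dose as baseline: expected difference in change = E7 − 0 = E7.
- Day 1 post-dose as baseline: expected difference in change = E7 − E1.

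Write E1 = f × E7, where f is the share already present at 2 hours. The second quantity becomes (1 − f) × E7. It is zero when f = 1, that is, when engagement is full at 2 hours and maintained.

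**2. A numerical example (assumed values).** Active arm: pre-dose 100, Day 1 at 2 hours 40, Day 7 at 2 hours 40. Change from pre-dose = 40 − 100 = −60. Change from Day 1 post-dose = 40 − 40 = 0.

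**3. Can f be found in the documents?** No. The EC50 is blacked out, which is not a fault of the plan, and the speed of marker response is not given. The protocol synopsis (Dose Selection Rationale) puts peak levels at 100 mg TID above the EC50 for RIP1 inhibition. That makes some effect at 2 hours plausible but does not fix its size.

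**4. Illustration over a range of f.** Assumptions: 30 patients per group, two-sample t-test, two-sided 0.05, the same SD of change under both baselines, and a true Day 7 effect of d SDs. The effect tested is d × (1 − f). Power (non-central t):

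| d | f = 0 | f = 0.5 | f = 0.8 | f = 1 |
|---|---|---|---|---|
| 0.5 | 0.48 | 0.16 | 0.07 | 0.05 |
| 0.8 | 0.86 | 0.33 | 0.09 | 0.05 |
| 1.0 | 0.97 | 0.48 | 0.12 | 0.05 |

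The f = 0 column is also the power with a Day 1 pre-dose baseline. Thirty per group is an upper bound, because PBMC are prepared only at equipped sites and the PK/PD set is restricted.

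**5. How many outputs are involved.** The t-test shell in PK/PD plan 7.1.2.2 has 22 single series plus 8 pRIP1/pMLKL series (plasma and PBMC, pre-dose and post-dose) = 30 series. Times 2 visits = 60 rows; times 3 p-value columns = 180 p-values. Post-dose: 4 series × 2 visits = 8 rows, and 8 × 3 = 24 p-values with no named baseline. Of these, 8 are within-control and have no drug effect to lose. The other 8 between-group and 8 within-active, 16 in all, could lose it.

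**6. Which baseline do the tests use?** The TFL list has four separate post-dose summary tables (7.1.2.1.24, .26, .28 and .30). The one summary shell shown, a pre-dose one, has a D1 block followed by change to D7 and to D14. Applied to the post-dose tables, that layout would make Day 1 post-dose the reference. Against this, the sentence in 6.4 is limited to plots, and Protocol 10.3 would give a value before the first dose. Neither reading is stated.

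**The case against.** Four arguments favour the plan.

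- **The plot rule is disclosed, and a time-matched contrast has its uses.** This stands in part. Day 7 or Day 14 minus Day 1 post-dose is a legitimate summary of change since the first dose. It is not an untreated comparison, and the match is incomplete: Day 1 is sampled around the first dose of the day, Days 7 and 14 around the second.
- **The general rules allow exceptions.** Correct. Protocol 10.3 applies in general, and main SAP 8.2 applies unless specified otherwise. The plot rule therefore breaches neither; the issue is what it estimates and how it is labelled.
- **The table layout points to each series using its own Day 1 value, and the D1 row would show what was subtracted.** This is a reasonable inference and softens the ambiguity. It is still not written down, and it is the reading under which the tests lose the effect.
- **Engagement is visible elsewhere.** Correct. Pre-dose change, raw post-dose summaries, mean-level plots and listings all remain.

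Stronger readings that a reader might infer are not supported:

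- **That the post-dose tests are shown to use the on-treatment baseline.** Their baseline is unnamed, not shown to be wrong.
- **That Protocol 8.4 removes the protocol's baseline rule for these markers.** The sentence "The PK analysis plan will supersede the protocol" stands in the PK section, directly after one on plasma concentrations, and does not clearly reach PD biomarkers.
- **That the mean-change plots, boxplots and heatmaps mix pre-dose and post-dose values.** Their list titles do not separate the two, but the figure shells are missing from the text and may do so.

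**Conclusion.** The point holds and is minor. For the post-dose plots it is certain: the stated baseline is on-treatment in the active arm and removes whatever engagement exists at 2 hours. For the post-dose tests and summary tables the finding is an unnamed baseline with two possible consequences, which exclude each other. Under one, 16 p-values could lose the effect; under the other, plots and tests disagree under one label.

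A reader might infer a definite loss of power from the table above. The documents do not support that: f, d and the equal SD are all assumed, and with slow marker onset f could be close to zero. These are exploratory secondary analyses, and the primary safety endpoint and the pre-dose (trough) tests are untouched.

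**What to change.** In PK/PD plan 6.4, state that the Day 1 pre-dose value is the baseline for both pre-dose and post-dose pRIP1/pMLKL change, and that this covers plots, summary tables and t-tests. If Day 7 or Day 14 minus Day 1 post-dose is kept, present it as supplementary and title it change in post-dose level since first dose. Label every pRIP1/pMLKL change output as pre-dose or post-dose. Reporting the Day 1 pre-dose to 2-hour change by arm would be a useful optional addition.

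The cost is one or two sentences plus titles or footnotes, made before unblinding. No new samples or assays are needed, because the Day 1 pre-dose sample is already collected for this assay.
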